6.1.5 Guidelines for continuation of treatment beyond tumor resection (Optional Phase 2)

Patients with positive PK and PD responses will be provided the option of continuing on therapy until tumor progression. PK data evaluates the drug concentration in enhancing and non-enhancing region of the tumor. PD analysis evaluates the biomarker response after 5-day treatment and compares this with archival tissue. If both are positive the patients will be enrolled into Phase 2 portion of the trial with the same dose level taken during Phase 0 (unless there is more than one DLT observed in Phase 2, see Section 4.1.2). If the PD data is not conclusive due to treatment effect or limited tissue samples from the surgery, the PK data would be the primary guidance on deciding phase 2 enrollment.

Some anticipated risks and safety considerations of the ribociclib+everolimus combination will be closely monitored. Preclinical and Phase I clinical data available from ongoing studies with ribociclib and everolimus separately suggest few overlapping toxicities for the proposed

Initial Version date: 10/16/2018

Revision date: 03/11/2019, 5/07/2019, 09/26/2019, 03/17/2020, 08/26/2024

combinations. Special attention will be paid to blood counts (cytopenias), mucositis, liver function test abnormalities and QTc prolongation. Clinical data from the [CLEE011X2101] study do not show marked accumulation in ribociclib with time, suggesting that it does not substantially inhibit its own metabolism or clearance. Everolimus and ribociclib are *in vitro* inhibitors and substrates of CYP3A4, and the latter is also a time-dependent CYP3A4 inactivator. The available preclinical and clinical data therefore suggest the possibility of a drug interaction, specifically one that may increase exposure to everolimus. Based on simulation using Simcyp software (Simcyp Version 12, release 1), the projected increase in the AUC_{0-6h} of everolimus was 3.5-fold following the starting daily dose of 200 mg ribociclib co-administered with 2.5 mg of everolimus for 14 days. No significant effect on ribociclib metabolism was predicted when co-administered with everolimus. Appropriate eligibility criteria, dose modification guidelines and stopping rules are included in this protocol.

6.1.6 Treatment duration

All Phase 0 patients will receive a 5-day regimen as described above. Patients with Rb+ mTOR+ tumors will be provided the option of continuing on therapy until tumor progression. In Phase 2 continuation therapy, patients will receive RP2D daily schedule (28 day cycle).

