Aberrant mitogenic PI3K/mTOR signaling and cell cycle control are hallmarks of human cancers. In GBMs, activating mutations in PI3K/mTOR pathway including PIK3CA and mTOR as well as loss-of-function mutations/deletions in PTEN are found in approximately 56% of the patients. The pathway induces uncontrolled proliferation by activating D-type cyclins. Together D-type cyclins and cyclin-dependent kinases (CDK) 4/6 form complexes crucial for cell cycle progression, specifically the G1-S phase transition. These complexes phosphorylate Rb, a product of the retinoblastoma protein tumor suppressor gene. In its active form, hypophosphorylated pRb is bound to E2Fs inhibiting their transcriptional activity. Hyperphosphorylation of pRb renders it inactive and allows for the release of E2F transcription factors necessary for initiation of S-phase and cell cycle progression. An endogenous CDK4/6 inhibitor, p16INK4A, negatively regulates these processes and is frequently mutated in GBMs (~40%) ([Verhaak et al., 2010](#)). In recent years there have been numerous clinical trials in adults with cancer utilizing small molecule inhibitors targeting cell cycle regulatory genes such as CDKs. Ribociclib in particular has been approved recently by FDA to treat breast cancer patients. Combination therapy with ribociclib and everolimus is currently on-going in several solid cancers. However, combination therapy with CDK inhibitor and mTOR inhibitor have yet to be evaluated in adult high-grade glioma patients. Abundant preclinical evidence indicates that Rb-deficient cancer cells are resistant to CDK4/6 inhibition and ongoing trials with CDK4/6 inhibitors exclude patients with Rb-deficient tumors. Patients with Rb+ and mTOR+ will be selected in the trial to ensure maximal benefit from the combination therapy.

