Due to persistent negative PK effects from everolimus, despite no adverse events limiting drug dosing, additional dose-levels will employ a single, high-dose administration of everolimus. Other combination drug studies have suggested 70mg weekly as a maximal-tolerated dose. As a lead-in to this combination dose in our study, a new dose level at 50mg once prior to surgery (in combination with 600mg ribociclib) will be introduced. This lead-in dose will give rise to 60mg at the next level and 70mg at the final level. Similarly, the phase 2 component of the study will reflect this new dosing regimen for patients with PK and PD effects from both drugs. Specifically, a lead-in regimen at 50mg q weekly in Phase 2 (in combination with ribociclib) will then be escalated towards 70mg weekly.

3 Objectives and endpoints

	Objective	Endpoint
Primary	
• To determine the dose-limiting toxicity (DLT) and maximum tolerated dose (MTD) for study drug when administered in combination.• To identify recurrent high-grade glioma patients with positive PK and PD effects.	
• MTD: highest dose of drug that did not cause a DLT in > 17% of participants• PK: total and unbound ribociclib and everolimus concentrations in non-enhancing and contrast-enhancing tumor tissue samples• PD: pRB-positive cells and pS6-positive cells
Secondary	
• To explore safety and efficacy in recurrent high-grade glioma patients with demonstrated PK and PD effects and determine RP2D• To describe PK for Phase 2 patients	
• Progression-free survival (PFS)• Overall survival (OS)• Drug-related toxicity• RP2D• Systemic PK profiles of ribociclib and everolimus when combined.
Exploratory	
• To explore evidence for CDK4/6 and mTOR pathway activity in tumor tissue (as compared to	
• Quantification of total and phosphorylated forms of Rb, FoxM1, S6, 4EBP, as well as cleaved Caspase-3 and MIB1. Expression of Cyclin D1,

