4.1.2 Phase 2 Dose expansion

Patients with tumors demonstrating favorable PK and PD will proceed to Phase 2 Dose Expansion. In Dose Levels 1-3, patients will continue treatment with the same treatment level as given in Phase 0, patients should take the treatment continuously in 28d cycles with 3 weeks on / 1 week off after surgery. In Dose Level 4+, patients should take everolimus in one dose weekly; ribociclib will be taken for 21 consecutive days followed by 1 rest week. The dose will be per Table 7. If more than one DLT is observed in 6 patients in the Phase 2 dose expansion, the enrollment will be stopped and the previous lower dose level will be considered the RP2D and will be given for the remaining patients enrolled. If more than one DLT is occurred with the Level 0, the study will be stopped due to toxicity. Typically DLTs are defined by 1 cycle of treatment, which is 28 days. Since Phase 0 treatment is given for only 5 days, Phase 0 dose escalation will only be determined by Phase 0 DLT rules unless determined otherwise by the DSMB. Patients will be treated until unacceptable toxicity is observed, or until disease progression as assessed by radiographic or clinical metrics. Preliminary rates of progression-free survival in patients with high-grade gliomas treated with ribociclib+everolimus will be measured through radiographic and clinical response metrics, specifically Response Assessment in Neuro-Oncology (RANO) criteria and investigator discretion. Phase 2 participants will return to the clinic to monitor safety per the schedule of events until treatment is ended and will then be contacted approximately every 3 months by letter or phone for collection of survival data. The start of follow up for long-term survival begins following completion of the Day 30 safety follow up call.. All Phase 0/2 participants will be followed for survival for up to 5 years.

Common Toxicity Criteria Adverse Event (CTC AE 4.03) will be utilized to review ribociclib+everolimus treatment effects in patients with brain tumors.

Trough steady-state blood samples will be obtained on days 1, 8, 15, and 22 of cycles 1 and 2 prior to the administration of ribociclib+everolimus on that day. Note: ribociclib+everolimus will be administered in the clinics on the clinic visit days to ensure the collection of trough level samples.

PHASE 2 STUDY				
	Cycle 1 (28 d)	Cycle 2 (28d)	Subsequent cycles (28d)	End of study
Day of cycle	D1, D8, D15, D22	D1, D8, D15, D22	N/A	N/A

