5.2 Inclusion criteria

Patients eligible for inclusion in this early treatment protocol have to meet **all** of the following criteria:

1. Prior resection of histologically-diagnosed WHO Grade III or IV glioma.
 - A. Glioma patients who have progressed on or following standard (Stupp regimen) therapy, which included maximal surgical resection, temozolomide, and fractionated radiotherapy.
2. Recurrence must be confirmed by diagnostic biopsy with local pathology review or contrast-enhanced MRI.
3. Subjects must have measurable disease preoperatively, defined as at least 1 contrast-enhancing lesion, with 2 perpendicular measurements of at least 1 cm, as per RANO criteria.
4. For gliomas, archival tissue must demonstrate: (a) RB positivity ($\geq 20\%$) on immunohistochemistry OR no RB mutations on next-generation sequencing (NGS), (b)

Initial Version date: 10/16/2018

Revision date: 03/11/2019, 5/07/2019, 09/26/2019, 03/17/2020, 08/26/2024

Chromosomal loss of CDKN2A/B/C OR CDK4/6 or CCND1/2 amplification on array CGH, (c) mTOR+: PTEN loss OR PIK3C2B or AKT3 amplification on aCGH OR mutations for PIK3CA or PIK3R1, or mTOR or PTEN mutations using rhAMP analysis or pS6 positivity on immunohistochemistry ($\geq 10\%$ for pS6). If mutations within the mTOR/PI3K pathways cannot be accurately detected due to poor tissue quality the enrollment criteria will be determined using RB and pS6 positivity.

5. Eastern Cooperative Oncology Group (ECOG) performance status ≤ 2 ([Appendix 1](#)).
6. Patients ≥ 18 years of age.
7. Ability to understand and the willingness to sign a written informed consent document (personally or by the legally authorized representative, if applicable).
8. Patient has voluntarily agreed to participate by giving written informed consent (personally or via legally-authorized representative(s), and assent if applicable).

(Written informed consent for the protocol must be obtained prior to any screening procedures. If consent cannot be expressed in writing, it must be formally documented and witnessed, ideally via an independent trusted witness.)

9. Willingness and ability to comply with scheduled visits, treatment plans, laboratory tests and other procedures.
10. Confirmed negative serum pregnancy test (β -hCG) before starting study treatment or patient has had a hysterectomy.
11. Patient has adequate bone marrow and organ function as defined by the following laboratory values (as assessed by the local laboratory for eligibility):

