5.3 Exclusion criteria

Patients eligible must not meet **any** of the following criteria:

1. Archival tissue is not available for research use or there is not a sufficient quantity available to confirm eligibility.
2. Archival tumor is not Rb-positive status and mTOR-positive status.
3. Patient has not received prior radiotherapy.
4. Co-morbid condition(s) that, at the opinion of the investigator, prevent safe surgical treatment.
5. Active infection or fever $> 38.5^{\circ}\text{C}$ that in the opinion of the investigator would be a safety risk to the patient.
6. Active (acute or chronic) or uncontrolled severe infection, liver disease such as cirrhosis, decompensated liver disease, and active and chronic hepatitis (i.e. quantifiable HBV-DNA and/or positive HbsAg, quantifiable HCV-RNA).
7. Known severely impaired lung function (spirometry and DLCO 50% or less of normal and O₂ saturation 88% or less at rest on room air).
8. Active, bleeding diathesis.
9. Patients with known hypersensitivity to any of the excipients of ribociclib or mTOR inhibitors (sirolimus or everolimus), including peanut, soy and lactose.
10. Patients with a clinically significant hypersensitivity to everolimus or to other rapamycin derivatives.
11. Prior therapy with ribociclib or any CDK4/6 inhibitor (e.g. palbociclib, abemaciclib), or with everolimus. Prior therapy is defined as a therapeutic dosing.
12. Patient who has received radiotherapy ≤ 4 weeks or limited field radiation for palliation ≤ 2 weeks prior to starting study drug, and who has not recovered to grade 1 or better from related side effects of such therapy (exceptions include alopecia or other toxicities not considered a safety risk for the patient at investigator's discretion) and/or in whom $\geq 25\%$ of the bone marrow (Ellis, 1961) was irradiated.
13. Patient has a concurrent malignancy or malignancy within 3 years prior to starting study drug, with the exception of adequately treated, basal or squamous cell carcinoma, non-melanomatous skin cancer or curatively resected cervical cancer.
14. Patient has impairment of gastrointestinal (GI) function or GI disease that may significantly alter the absorption of the study drugs (e.g., ulcerative diseases, uncontrolled nausea, vomiting, diarrhea, malabsorption syndrome, or small bowel resection).
15. Patient has a known history of HIV infection (seropositivity; testing not mandatory).

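### Section 6.1.6 offers Phase 2 continuation on Rb+ mTOR+ status, which every enrolled patient already has, while 4.1.2 and 6.1.5 require favorable PK and PD; the analysis section does not settle whom PFS and OS describe

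*Combined protocol and SAP*

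**What the plan says.** **Entry to Phase 2.** Section 4.1.2 states: "Patients with tumors demonstrating favorable PK and PD will proceed to Phase 2 Dose Expansion". Section 6.1.5, which deals specifically with treatment after resection, agrees: "Patients with positive PK and PD responses will be provided the option of continuing on therapy until tumor progression". It adds one exception. Where PD cannot be judged because of treatment effect or too little tissue, "the PK data would be the primary guidance on deciding phase 2 enrollment". Section 6.1.6, on treatment duration, makes the same offer to a different group: "Patients with Rb+ mTOR+ tumors will be provided the option of continuing on therapy until tumor progression". It attaches no PK or PD condition.

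**Entry to the trial.** Exclusion criterion 2 in 5.3 reads: "Archival tumor is not Rb-positive status and mTOR-positive status". Inclusion criterion 4 in 5.2 sets the marker requirements on archival tissue. Where poor tissue prevents mutation testing, "the enrollment criteria will be determined using RB and pS6 positivity". Section 2.1 gives the intent: "Patients with Rb+ and mTOR+ will be selected in the trial to ensure maximal benefit from the combination therapy".

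**Objective and analysis.** The secondary objective in Section 3, repeated in 9.6, is: "To explore safety and efficacy in recurrent high-grade glioma patients with demonstrated PK and PD effects and determine RP2D". Section 9.7.1 defines positive PK (unbound concentrations of both drugs in non-enhancing tumor above their in vitro IC50) and positive PD (a fall of more than 30% in both pRB-positive and pS6-positive cells). It then plans Kaplan-Meier summaries of PFS and OS without saying which patients are included. Section 9.3.1 carries the title Full Analysis Set but does not define one.

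**The concern.** Rb+ mTOR+ status is settled on archival tissue before the first dose. Used again after surgery, it cannot separate patients who should continue from those who should not. Taken literally, 6.1.6 therefore extends the offer to every enrolled patient and contradicts the two sections that require favorable PK and PD.

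Two things depend on which sentence a site follows: who is offered treatment until progression, and whom the Phase 2 PFS, OS and toxicity results describe. The difference could be large in this trial. Section 2.3 reports that four patients at the first dose had almost no detectable everolimus in brain or CSF and no PD effect of either drug, and it goes on to describe persistently negative everolimus PK.

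A smaller gap remains even if 6.1.6 is set aside. A patient who enters on PK alone has no demonstrated PD effect and so falls outside the secondary objective as worded. Nothing in Section 9 keeps such patients apart from those positive on both. The RANO evaluability rule in 7.1.1.8 (at least one cycle and a Phase 2 MRI) does not do so either.

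**Working it through.** **Inputs, all from Section 9.7.1 unless noted**
- Phase 0 size: 6 to 32.
- Share of Phase 0 patients with PK/PD responses: at most 50%.
- Expected Phase 2 size: 3 to 12.
- About 8 patients in each of three time cohorts, so 3 × 8 = 24.
- Drop-out 20%; total about 30.
- Share eligible under 6.1.6: 100%, from 5.2 and 5.3.

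**Step 1: the plan's own Phase 2 figure.** Phase 2 size = PK/PD-positive share × Phase 0 size.
- Lower end: 0.5 × 6 = 3, which reproduces.
- Upper end: 0.5 × 32 = 16, which does not reproduce the stated 12.
- On a base of 24: 0.5 × 24 = 12, and 24 / (1 − 0.20) = 30, which matches the stated total.

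The 12 therefore fits a base of 24 and not the 32 in the same paragraph. For this reason the comparison below starts from Phase 0 size and does not scale up the stated 3 to 12.

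**Step 2: numbers eligible under each rule.**

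| Phase 0 size | Eligible under 6.1.6 (100%) | PK- and PD-positive (at most 50%) | Eligible under 6.1.6 but not positive on both (at least) |
|---|---|---|---|
| 6 | 6 | 3 | 3 |
| 24 | 24 | 12 | 12 |
| 32 | 32 | 16 | 16 |

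Because 50% is a ceiling, the ratio is at least 1 / 0.5 = 2, and at least 1 − 0.5 = 50% of those eligible under 6.1.6 would lie outside the secondary-objective population.

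**Step 3: a lower response rate.** The documents give no observed rate. If it is assumed to lie between 10% and 50%, then at a Phase 0 size of 32 the number belonging to the secondary-objective population runs from 0.1 × 32 = 3.2 to 0.5 × 32 = 16, while 6.1.6 still makes all 32 eligible.

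**Step 4: the PK-led exception.** Its size would be Phase 0 size × rate of inconclusive PD × rate of positive PK among those patients. Neither rate is given, so no figure can be put on it.

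**Step 5: consistency with the rest of the plan.** Section 4.1.1 arranges survival follow-up for Phase 0 patients who do not go on to Phase 2. Section 9.7.2 expects about half of Phase 0 to enroll. Section 2.3 describes the revised Phase 2 dosing as being for patients with PK and PD effects of both drugs. Each assumes a narrower rule than the one in 6.1.6.

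**The case against.** The best defence is that the intended rule is not in real doubt. Section 6.1.6 concerns duration, follows directly after the section written to govern Phase 2 entry, and is outnumbered by 4.1.2, 6.1.5, the secondary objective and the sizing assumption. It may be leftover wording. This stands as an account of how the sentence arose, and it limits the claim: the Phase 2 population may differ from the stated one, but nothing shows that it will. It does not remove the conflict, because 6.1.6 is current text in the treatment section and sets no PK or PD condition.

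A reader might infer three competing entry rules. The documents do not support that. The PK-led route is a conditional exception inside 6.1.5, and the direct conflict is between 6.1.6 and the other two sections.

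A reader might also infer that Phase 2 would double, to about 6 to 24. That treats eligibility as enrollment, although 6.1.6 offers only an option. It also builds on an upper figure of 12 that does not follow from half of 32.

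Finally, Phase 2 is declared exploratory with no formal comparison, and PK and PD are primary endpoints in Phase 0, so patients positive on both can be identified afterwards whoever continues. This is correct. The information is not lost, but the plan does not commit to using it to define the reported group.

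**Conclusion.** The conflict is real. Section 6.1.6 as written makes 100% of Phase 0 patients eligible to continue; the PK-and-PD rule, on the plan's own ceiling, makes at most 50% eligible. That is at least a twofold difference in eligibility at any Phase 0 size. It rests on two points: Rb+ mTOR+ status is an entry requirement without exception, as 5.2 and 5.3 state, and the 50% ceiling in 9.7.1 holds. A lower response rate would widen the gap.

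Actual entry may be lower than eligibility. The PK-only group cannot be sized. It would go too far to say that the secondary-objective population is lost, since it can be recovered from the Phase 0 results. What is missing is one stated entry rule and an analysis set that matches the objective.

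**What to change.** 1. The sponsor should reconcile 4.1.2, 6.1.5 and 6.1.6 so that the protocol states one Phase 2 entry rule, including what happens when PD is inconclusive. Which rule that should be is a clinical decision outside this review.
2. In 9.3.1 and 9.7.1, define the PFS/OS set for the secondary objective as patients with both positive PK and positive PD, using the definitions already in 9.7.1.
3. List patients who entered on PK alone, with PD inconclusive, separately for PFS and OS.
4. Keep all treated patients in the toxicity tables.

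The cost is a few sentences and no new data. The drawback is a smaller set for the main Phase 2 description, in a component planned at 3 to 12 patients. The PK-only group may be so small that a patient listing is all it supports.

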6.2 Dose modification post-tumor resection (Phase 2)

For patients who do not tolerate the protocol-specified dosing schedule, dose adjustments are permitted in order to allow the patients to continue the ribociclib+everolimus treatment. See [Table 10](#) for dose reductions. Any changes in ribociclib+everolimus administration must be recorded.

6.2.1 General guidelines for dose modifications

- For grade 1 and tolerable grade 2 treatment-related toxicities, with the exception of pneumonitis, patients may continue at the current dose of ribociclib+everolimus treatment.
- For intolerable grade 2 treatment-related toxicities as those that are irreversible (e.g., neurotoxicities, ocular toxicities, or cardiac toxicities) or prolonged grade 2 toxicities (i.e., those lasting longer than 14 days), or any grade 3 toxicities, with the exception of pneumonitis, dosing should be interrupted until resolution to grade 1 or lower followed by resumption of a new 28 days regimen. Dosing reductions could also be considered after grade 3 toxicities ([Table 11](#)).
- For any grade 4 toxicity, dosing should be interrupted and the patients should be followed until the toxicity resolution to baseline levels, grade 1, or become stable. Following recovery from grade 4 events, **no additional ribociclib+everolimus treatment** should be given to the patient except for neutropenia and thrombocytopenia (details in [Table 11](#)).

More detailed ribociclib and everolimus dose modification guidelines are described in Section [6.2.2](#) respectively for selected toxicities. Any variance from these guidelines in view of patient safety must first be discussed with the Sponsor unless there is an urgent need for action.

Initial Version date: 10/16/2018

Revision date: 03/11/2019, 5/07/2019, 09/26/2019, 03/17/2020, 08/26/2024

All dose modifications, interruptions or discontinuations must be based on the worst preceding toxicity as graded by the NCI Clinical Toxicity Criteria version 4.03.

Patients whose treatment is interrupted or permanently discontinued due to an AE must be followed until resolution or stabilization of the event. Patients with more than 1 interruption should be discontinued from ribociclib treatment.

